3. INVESTIGATIONAL PLAN

3.1 Study Design and Duration

This is an open label, multi-site, phase 1/2 study of encorafenib +/- binimatinib + nivolumab + ipilimumab for the treatment of participants with unresectable or metastatic *BRAF*-mutated melanoma in high risk cohorts.

Study participants will consist of metastatic melanoma patients harboring *BRAFV600E/K* mutation without previous frontline therapy or recently started treatment with up to 6 weeks of targeted therapy, or one cycle of immunotherapy (or >6 months from adjuvant therapy). Toxicity from prior treatment must have resolved to ≤ Grade 1 and not included previous Grade 3–4 irAEs that required treatment discontinuous or previous Grade 2 immune-related uveitis or pneumonitis.

Phase I, Cohort 1: Twelve patients will be treated with triple therapy: 300 mg encorafenib and 3mg/kg nivolumab and 1 mg/kg ipilimumab. Dose-limiting toxicity (DLT) for Cohort 1 will be evaluated at week 6.

[figure not shown]
Phase I, Cohort 2: Upfront quadruple therapy (450mg encorafenib, 45mg binimatinib, 3mg/kg nivolumab, and 1mg/kg ipilimumab) will be investigated with twelve patients. DLT for Phase I, Cohort 2 will be evaluated at week 6.

Prior studies with triplet therapies combining anti PD-1/PD-L1, *BRAF*, and MEK inhibition have shown Grade 3–4 AEs occurring from 58%–73%^{5,43,44,68}. These initial cohorts were small and did not use the newer, more potent and specific *BRAF*/MEK inhibitor pair encorafenib/binimatinib. We are allowing an initial DLT rate up to 75% in a continuous Bayesian monitoring protocol (See Statistics Section 8). We anticipate most of the toxicities to be additive and not synergistic and based on earlier recognition and treatment of immunotherapy AEs (see Appendix 6) and very specific AEs from encorafenib and binimatinib (see Appendix 2 and 3), we anticipate being able to create a safe RP2R dosing schedule.

Upon establishment of RP2R schedule, only participants with advanced melanoma who are either treatment naïve in the metastatic setting, have recently started treatment with targeted therapy within the past 6 weeks, or one cycle of immunotherapy, or who have progressed on adjuvant therapy more than 6 months following completion of adjuvant therapy (either *BRAF*-MEK or PD1 Ab) will be eligible for participation in high risk disease cohort expansion (Groups 1 or 2, see Schema below).

Phase II will take the RP2R schedule from Phase I and apply it to patients who may derive the most benefit from triple or quadruple therapy: Group 1) symptomatic brain metastases [up to 30 patients] and Group 2) LDH > 1x ULN with liver metastases OR bulky visceral disease (sum of longest diameter (SLD) > 44 mm) [up to 60 patients when combined with Group1].

Schema

Enrolled participants will be evaluated for safety and efficacy throughout the study and during follow up at the time points indicated on the time and events schedules presented in Tables 5.2.1 – 5.2.3. Response to treatment will be assessed in the intracranial (Group 1) and extracranial compartments (Group 2) and will be evaluated by serial radiographic assessment every 12 weeks until documented progression, withdrawal of consent, or the end of the study.

Follow-up Phase for each enrolled subject begins when the decision to discontinue a subject from study therapy is made (no further treatment with study therapy).

Participants will be followed for efficacy and OS. Treatment decisions will be based on local imaging evaluations using RANO-BM for intracranial lesions and RECIST 1.1 for extracranial lesions^{69,70}.

Additional imaging may be performed for patient care at the discretion of the investigator. All efficacy objectives will be based on Investigator assessment at the study site.

Safety will be evaluated for all treated participants using the NCI CTCAE version 5.0. Safety assessments will be based on medical review of AE reports, vital sign measurement results, physical examinations, and clinical laboratory tests.

3.1.1 Screening Phase

3. Screening begins by establishing the subject's initial eligibility and signing of the ICF.
4. The first 24 patients will be enrolled in the Phase I Cohort 1 (triple therapy with encorafenib, nivolumab, and ipilimumab) or Phase I Cohort 2 (upfront quadruple therapy of encorafenib, binimetinib, ipilimumab, and nivolumab)
5. After RP2R is determined, Phase II patients will be enrolled preferentially into Group 1 (brain metastases) if possible; otherwise if they meet criteria will be enrolled into Group 2 (liver metastases with bulky disease and/or elevated LDH), total enrollment goal is 60 between the two groups.

3.2 Post Study Access to Drug

At the end of the study, BMS will not continue to provide BMS supplied study drug to participants/investigators unless BMS chooses to extend the study. The investigator should ensure that the subject receives appropriate care to treat the condition under study. Participants who continue to respond at the end of on study treatment may be prescribed study medication through commercial supply.

3.3 Study Population

For entry into the study, the following criteria MUST be met.

3.3.1 *Inclusion Criteria*

1. Signed Written Informed Consent
 - a. Participants must have signed and dated an IRB/IEC approved written informed consent form in accordance with regulatory and institutional guidelines. This must be obtained before the performance of any protocol-related procedures that are not part of normal subject care.
 - b. Participants must be willing and able to comply with scheduled visits, treatment schedule, laboratory testing, and other requirements of the study.
2. Age ≥ 18 years
3. Histologically confirmed diagnosis of unresectable or metastatic melanoma
4. Presence of *BRAFV600E/K* mutation in tumor tissue as determined in a CLIA certified laboratory
5. Patients are required to submit archival biopsy material, if available, and submit research blood samples prior to first dose. Ten patients in each Phase I cohort will undergo fresh biopsy. These will be the first 10 unless medical or societal factors (e.g. COVID19) limit the pursuit of research biopsies.
6. Patients must be greater than 6 months from completion of adjuvant therapy (if any given) and/or treatment naïve in the metastatic setting or have recently started targeted therapy within the last 6 weeks, or one cycle of immunotherapy.
7. Prior radiotherapy must have been completed at least 2 weeks prior to study drug administration.
8. An ECOG Performance Status of 0 or 1. If enrolling in Group 1 of Phase II, can have Performance Status from 0-2.
9. Measurable disease by CT or MRI per RANO-BM (brain metastases) OR RECIST v1.1 criteria
10. Must have high risk features described as described in Phase II expansion cohort – EITHER brain metastases as described in Phase II Group 1 OR Elevated LDH/Bulky Visceral Disease as described in Phase II Group 2.

11. Adequate bone marrow, organ function, and laboratory parameters:

- a. ANC > 1.5×10^9 /L;
- b. Hemoglobin > 8 g/dL with or without transfusions;
- c. Platelet > 100×10^9 /L;
- d. Serum creatinine $\leq 1.5 \times$ ULN, OR calculated creatinine clearance > 50 mL/min by Cockcroft-Gault formula, OR estimated glomerular filtration rate > 50 mL/min/1.73 m²

12. Patient IS permitted to be on corticosteroids if related to disease burden and MAY have symptomatic brain lesions as long as radiation or surgical intervention is not deemed to be urgently necessary.

- a. Symptomatic intracranial metastases may be on steroids at a total daily dose of no higher than 4 mg of dexamethasone or equivalent that is stable or tapering for 10 days prior to first treatment,
- b. have no immediate need for SRT or surgery (within 3 week prior to first treatment),
- c. have a performance status of 0–2 and
- d. have had no experience of seizure within 10 days prior to first treatment.

13. Female patients of childbearing potential must have a negative serum β -HCG test result during screening prior to first dose

14. Females of childbearing potential must agree to protocol-approved methods of contraception, and to not donate Ova from Screening until 30 days of last dose of study drug.

15. Male patients must use contraception that is highly effective or acceptable, and not donate sperm from Screening until 90 days after the last dose of study drug.

16. The patient is deemed by the Investigator to have the initiative and means to comply with scheduled visits, treatment plan and study procedures.

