Ipilimumab has a terminal half-life of approximately 15.4 days. The expected in vivo degradation of monoclonal antibodies into small peptides and amino acids occurs via biochemical pathways that are independent of cytochrome P450 enzymes. The population pharmacokinetics (PPK) of ipilimumab was studied with 785 participants and demonstrated that PK of ipilimumab is linear and exposures are dose proportional across the tested dose range of 0.3 to 10 mg/kg, and the model parameters are time invariant. Upon repeated dosing of ipilimumab, administered every three weeks, minimal systemic accumulation was observed by an accumulation index of 1.5-fold or less and ipilimumab steady-state concentrations were achieved by the third dose. The ipilimumab clearance of 16.8 mL/h from the PPK analysis is consistent with that determined by PK analysis. The terminal half-life (T-HALF) and Vss of ipilimumab calculated from the model were 15.4 days, and 7.47 L, which are consistent with that determined by non-compartmental analysis (NCA). Volume of central (Vc) and peripheral compartment were found to be 4.35 L and 3.28 L, respectively, suggesting that ipilimumab first distributes into plasma volume and subsequently into extracellular fluid space. Clearance of ipilimumab and Vc were found to increase with an increase in body weight. Nevertheless, there was no significant increase in exposure with increase in body weight when dosed on a mg/kg basis, supporting dosing of ipilimumab based on a weight normalized regimen. Additional details are provided in the ipilimumab Investigator Brochure (IB).

Encorafenib

Encorafenib is administered orally with 85% bioavailability, reaching maximum post-dose concentration in 2 h with a 6-h half-life. Food intake delays absorption of the medication but does not alter overall absorption. It is metabolized by cytochrome 450 enzymes (CYP3A4, CYP2C19, and CYP2D6) and 20 unique metabolites have been identified, which are excreted equally in urine and feces. Furthermore, 2% and 5% of the absorbed medication is excreted unchanged in urine and feces, respectively ²⁹.

Binimetinib

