3.5 Discontinuation of Participants from Treatment with Study Drugs

Participants MUST discontinue investigational product (and non-investigational product at the discretion of the investigator) for any of the following reasons:

- Subject's request to stop study treatment
- Any clinical AE, laboratory abnormality or intercurrent illness which, in the opinion of the investigator, indicates that continued participation in the study is not in the best interest of the subject
- Pregnancy
- Loss of ability to freely provide consent through imprisonment or involuntarily incarceration for treatment of either a psychiatric or physical (eg, infectious disease) illness
- Additional protocol specified reasons for discontinuation (see Section 4.3.5)

All participants who discontinue investigational product should comply with protocol specified follow-up procedures as outlined in Section 5 - Study Assessment and Procedures. The only exception to this requirement is when a subject withdraws consent for all study procedures including post-treatment study follow-up or loses the ability to consent freely (ie, is imprisoned or involuntarily incarcerated for the treatment of either a psychiatric or physical illness). If study treatment is discontinued prior to the subject's completion of the study, the reason for the discontinuation must be documented in the subject's medical records and entered on the appropriate case report form (CRF) page.

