4.5 Selection and Timing of Dose for Each Subject

Dosing and schedules for QUAD-01 are outlined in Table 4.5A and 4.5B. The investigational products nivolumab at 3mg/kg and ipilimumab at 1mg/kg will be given every 3 weeks for the first 4 treatments, then switched to single agent nivolumab at 480mg flat dose for up to one year. Encorafenib with or without binimatinib will be dosed as shown in Table 4.5A.

Table 4.5A: Dosing Schedule for Phase I

	Day 1 Week 1	Day 1 Week 2	Day 1 Week 3	Day 1 Week 4	Day 1 Week 5	Day 1 Week 6	Day 1 Week 7
Cohort 1: Triple therapy (encorafenib + nivolumab + ipilimumab)	300 mg encorafenib PO daily						
	3mg/kg Nivolumab			3mg/kg Nivolumab			3mg/kg Nivolumab
	1mg/kg Ipilimumab			1 mg/kg Ipilimumab			1 mg/kg Ipilimumab
Cohort 2: Quadruple therapy (encorafenib + binimetinib + nivolumab + ipilimumab)	450 mg encorafenib PO daily						
	45 mg binimetinib PO BID						
	3mg/kg Nivolumab			3mg/kg Nivolumab			3mg/kg Nivolumab
	1mg/kg Ipilimumab			1 mg/kg Ipilimumab			1 mg/kg Ipilimumab

*Investigational products nivolumab and ipilimumab will be administered every 3 weeks for the first four doses, then single agent nivolumab will be administered every 4 weeks at flat dose of 480mg for up to one year.

Phase I/II study of encorafenib and binimetinib with nivolumab and low dose ipilimumab in metastatic *BRAF* mutant melanoma

Table 4.5B: Dosing Schedule for Phase II

	Day 1 Week - 2	Day 1 Week - 1	Day 1 Week 1	Day 1 Week 2	Day 1 Week 3	Day 1 Week 4	Day 1 Week 5
Group 1: Brain metastases	RP2R	RP2R	RP2R	RP2R	RP2R	RP2R	RP2R
Group 2: Elevated LDH OR Bulky Visceral Disease SLD > 44 mm	RP2R	RP2R	RP2R	RP2R	RP2R	RP2R	RP2R

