4.6 Concomitant Therapy

All concomitant medications and treatments (including over-the-counter or prescription medicines, vitamins, vaccines and/or herbal supplements) must be recorded in the eCRF and medical records. Details regarding all prior anticancer treatment will also be recorded in the eCRF and medical records.

Any medication received within 28 days before the first dose of study treatment and within 30 days after the last dose of study treatment, or until the patient begins a new anticancer therapy, whichever occurs first, will be recorded in the eCRF and medical records. Any addition, deletion or change in the dose of these medications will also be recorded. Details of prior antineoplastic treatments including number of prior metastatic regimens will also be recorded.

Unless specifically prohibited, concomitant medications may be administered at the Investigator's discretion to manage the patient's medical condition and to conform to standard practice during the Treatment Period.

Any medication or vaccine (including over-the-counter or prescription medicines, vitamins and/or herbal supplements) that the patient is receiving at the time of enrollment or receives during the study must be recorded along with:

- a. Reason for use.
- b. Dates of administration including start and end dates.
- c. Dosage information (using generic drug names when possible), including dose and frequency.

Immunotherapy

Nivolumab and Ipilimumab are monoclonal antibodies that are cleared by catabolic processes and do not have drug-drug interaction guidelines.

Targeted therapy

Encorafenib

Encorafenib is a reversible inhibitor of CYP2B6, CYP2C9, CYP3A4 and UGT1A1. It is also a time-dependent inhibitor of CYP3A4 and induced CYP2B6, CYP2C9 and CYP3A4 in human primary hepatocytes. Permitted medications to be used with caution in this study include those that are sensitive substrates of CYP2B6, CYP2C9, CYP3A4 and UGT1A1 or those substrates that have a narrow therapeutic index.

There is a potential for encorafenib to induce CYP3A4, which may reduce the effectiveness of hormonal contraception methods. Therefore, the use of at least 1 form of non-hormonal contraception is required for females of childbearing potential during participation in this study. Caution should be used in patients receiving concomitant treatment with other drugs that are substrates of CYP3A4 as the efficacy of these drugs could be reduced when administered with encorafenib.

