 - Dosing delays to allow for prolonged steroid tapers to manage drug-related AEs are allowed. Prior to re-initiating treatment in a subject with a dosing delay lasting > 6 weeks from the previous dose, the Study PI must be consulted. Tumor assessments should continue as per protocol even if dosing is delayed. Periodic study visits to assess safety and laboratory studies should also continue every 6 weeks or more frequently if clinically indicated during such dosing delays.
 - Dosing delays lasting > 6 weeks from the previous dose that occur for non-drug-related reasons may be allowed if approved by the Study PI. Prior to re-initiating treatment in a subject with a dosing delay lasting > 6 weeks, the Study PI must be consulted. Tumor assessments should continue as per protocol even if dosing is delayed. Periodic study visits to assess safety and laboratory studies should also continue every 6 weeks or more frequently if clinically indicated during such dosing delays.

- Any AE, laboratory abnormality, or intercurrent illness which, in the judgment of the Investigator, presents a substantial clinical risk to the subject with continued nivolumab or ipilimumab dosing.

Note: If a subject experiences a severe AE during induction treatment (ie, the combination of nivolumab and ipilimumab) that requires discontinuation from further treatment with the combination, continuing treatment with nivolumab monotherapy may be considered contingent on discussion with and approval by the Study PI.

Exceptions to Permanent Discontinuation of study drug dosing under the following situations:

- Potentially reversible inflammation (< Grade 4), attributable to a local anti-tumor reaction and a potential therapeutic response. This includes inflammatory reactions at sites of tumor resections or in draining lymph nodes, or at sites suspicious for, but not diagnostic of metastasis.
- Participants with the following conditions where in the investigator's opinion continuing study drug administration is justified:
 - Endocrinopathies where clinical symptoms are controlled with appropriate hormone replacement therapy.

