6.3 Pregnancy

If, following initiation of the study drug, it is subsequently discovered that a study subject is pregnant or may have been pregnant at the time of study exposure, including during at least 5 half-lives after product administration, the investigator must immediately notify the BMS Medical Monitor/designee of this event and complete and forward a Pregnancy Surveillance Form to BMS Designee within 24 hours and in accordance with SAE reporting procedures described in Section 6.1.1. In most cases, the study drug will be permanently discontinued in an appropriate manner (eg, dose tapering if necessary, for subject safety). In the rare event that the benefit of continuing study drug is thought to outweigh the risk, after consultation with BMS, the pregnant subject may continue study drug after a thorough discussion of benefits and risk with the subject Protocol-required procedures for study discontinuation and follow-up must be performed on the subject unless contraindicated by pregnancy (eg, x-ray studies). Other appropriate pregnancy follow-up procedures should be considered if indicated. The investigator must immediately notify the BMS (or designee) Medical Monitor of this event and complete and forward a Pregnancy Surveillance Form to BMS (or designee) within 24 hours and in accordance with SAE reporting procedures described in Section 6.1.1. Follow-up information regarding the course of the pregnancy, including perinatal and neonatal outcome and, where applicable, offspring information must be reported on the Pregnancy Surveillance Form.

Any pregnancy that occurs in a female partner of a male study participant should be reported to BMS. Information on this pregnancy will be collected on the Pregnancy Surveillance Form

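### Women's 30-day post-dose limit in inclusion criterion 14 can end up to 47 days before the 77-day ipilimumab exposure window implied by Section 6.3

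*Combined protocol and SAP*

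**What the plan says.** Criterion 14 in Section 3.3.1 requires that women able to conceive "must agree to protocol-approved methods of contraception, and to not donate Ova from Screening until 30 days of last dose of study drug". Criterion 15, for men, requires contraception and that they "not donate sperm from Screening until 90 days after the last dose of study drug".

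Section 6.3 requires the investigator to report a pregnancy if the participant may have been pregnant at the time of study exposure, "including during at least 5 half-lives after product administration". Section 1.4.1.1 states: "Ipilimumab has a terminal half-life of approximately 15.4 days".

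Other contraception text gives no post-dose period. Section 4.6 says that "the use of at least 1 form of non-hormonal contraception is required for females of childbearing potential during participation in this study", and its reason is that encorafenib may induce CYP3A4 and weaken hormonal methods. Section 3.3.4 defines childbearing potential but sets no duration.

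On dosing, Section 4.5 gives nivolumab plus ipilimumab every 3 weeks for four doses, "then single agent nivolumab will be administered every 4 weeks at flat dose of 480mg for up to one year". Section 3.5 covers stopping: "Participants MUST discontinue investigational product (and non-investigational product at the discretion of the investigator) for any of the following reasons". After a severe adverse event in induction, Section 4.10 says that "continuing treatment with nivolumab monotherapy may be considered contingent on discussion with and approval by the Study PI".

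**The concern.** The 30-day clock starts at the last dose of any study drug and takes no account of which drug that was. For a woman who completes induction and spends months on nivolumab maintenance, ipilimumab is long past by the time the clock starts. For a woman who stops everything during induction, the clock starts while ipilimumab exposure is recent. The limit thus gives least cover where ipilimumab exposure is most recent.

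Such a woman could follow criterion 14 as naturally read, conceive after day 30, and at once be a reportable exposed pregnancy under Section 6.3. The schedules in Section 5.1 list a pregnancy test at screening only, so the contraception period is the main safeguard after treatment. If the 30 days is instead read as applying to ova donation alone, sites have no post-dose contraception period to give her.

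**Working it through.** **Inputs**

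- Post-dose limit for women: 30 days after the last dose of study drug (criterion 14).
- Post-dose limit for men: 90 days (criterion 15).
- Exposure window: at least 5 half-lives after administration (Section 6.3).
- Ipilimumab half-life: 15.4 days (Section 1.4.1.1).
- Encorafenib half-life: 6 hours (Section 1.4.1.1).
- Nivolumab half-life: not given, so a range is assumed below.

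The protocol does not state an ipilimumab window in days, so there is no printed figure to reproduce.

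**Ipilimumab**

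Window = 5 x 15.4 = 77 days.

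Let d be the number of days from the last ipilimumab dose to the last dose of any study drug. The limit then ends on day d + 30, and

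gap = 77 - (d + 30) = 47 - d days, or zero if that is negative.

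| All study drug stops | d | 30-day limit ends on day | Gap (days) |
|---|---|---|---|
| With the last ipilimumab dose | 0 | 30 | 47 |
| 2 weeks later | 14 | 44 | 33 |
| 3 weeks later | 21 | 51 | 26 |
| After one maintenance nivolumab dose (4-week interval assumed) | 28 | 58 | 19 |
| Break-even | 47 | 77 | 0 |
| After two maintenance doses | 56 | 86 | 0 |

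At 30 days, 30 / 15.4 = 1.95 half-lives have passed and about 26% of the drug remains (0.5^1.95). At 5 half-lives about 3.1% remains (0.5^5).

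**Sensitivity to the half-life**

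The same section gives clearance 16.8 mL/h and steady-state volume 7.47 L. A one-compartment calculation, which is a lower bound for the terminal half-life, gives ln 2 x 7.47 / 0.0168 = 308 hours, or 12.8 days. Five of those are 64 days, still more than twice the 30-day limit.

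**Other drugs**

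- Encorafenib: 5 x 6 hours = 30 hours, so 30 days is ample.
- Nivolumab: any half-life above 30 / 5 = 6 days makes the window longer than 30 days. If it is assumed to be 10 to 30 days, the window is 5 x 10 = 50 to 5 x 30 = 150 days. The gap is then 20 to 120 days when nivolumab is the last drug, and smaller if encorafenib continues.

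**Men**

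90 - 77 = 13 days of margin, so criterion 15 already covers the ipilimumab window.

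**Can d be small in practice?**

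Yes. The synopsis anticipates dose-limiting toxicity in up to 30–50% of participants, and the evaluation period is weeks 1 to 6, inside induction. Section 3.5 allows the targeted drugs to be stopped along with the antibodies, and Section 4.10 makes nivolumab alone conditional on approval. Not every dose-limiting toxicity ends all treatment, so that percentage is not the share of women affected.

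**The case against.** The strongest reply is that Section 4.6 already protects these women. It requires non-hormonal contraception throughout participation. Sections 3.6 and 3.6.1 say that people who stop treatment stay in the study and are followed until death or study conclusion, and safety follow-up runs to 100 days. On that reading a woman at day 77 is still bound. This does not succeed. The sentence belongs to an encorafenib drug-interaction paragraph and has no end date. Stretching it over the whole of follow-up would leave criterion 14's 30-day limit with no work to do as a contraception limit. At best it shows two clauses that need reconciling.

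Second, Section 6.3 is a notification rule, and nothing in the protocol says contraception must last five half-lives. A reporting window may reasonably be the wider of the two. That stands as far as it goes: the two sections do not contradict each other. The five-half-life window is used here only as the protocol's own measure of how long a dose counts as exposure.

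Third, the 47-day figure depends on the 30 days applying to contraception. That also stands. On the donation-only reading the defect is a missing period, which is no better for the participant.

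Fourth, the group is small: women of childbearing potential, in a trial of at most 84 people, who stop all drugs within 47 days of the last ipilimumab dose. Section 4.7 lets the investigator hold one drug class and continue the other, which would often close the gap. This stands, and the number affected cannot be estimated from the documents.

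Finally, the consent form and Investigator Brochures are not available here and may already say more. That cannot be checked; the eligibility criterion should still be right in itself.

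**Conclusion.** The concern holds and should be fixed. As naturally read, criterion 14 releases a woman who stops all study drug early up to 47 days before the ipilimumab exposure window closes; the gap is 47 - d days and is zero from d = 47. Because Section 6.3 says at least five half-lives, 77 days is a minimum.

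The result rests on the protocol's 15.4-day half-life and on reading the 30 days as covering contraception, in parallel with criterion 15. The nivolumab gap of 20 to 120 days rests on an assumed half-life and is indicative only. This is a participant-safety point, with no bearing on any estimate, error rate or stopping rule.

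**What to change.** Reword criterion 14 so that one end date, set by drug, governs both obligations. For example:

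> Females of childbearing potential will use protocol-approved contraception and will not donate ova, from Screening until the latest of: (a) 30 days after the final encorafenib or binimetinib dose; (b) at least 77 days (5 half-lives) after the final ipilimumab dose; (c) 5 half-lives after the final nivolumab dose, with the number of days taken from the current Investigator Brochure.

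Check the 77 days against the current ipilimumab Brochure at the same time, and lengthen it if the Brochure requires. Put the same wording in the consent form. Criterion 15 and Section 6.3 need no change on this ground.

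The cost is amendment text, a consent update and a longer contraception obligation for some women after treatment. Sample size, monitoring and analysis are unaffected.
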